DESIGN EPOC is designed to examine the feasibility of conducting point-of-care (POC) tests for SARS-CoV-2 antibodies and compare the reproducibility of these tests to tests run at a central laboratory on specimens obtained from the same study participants at the same time. This will involve recruiting 375 individuals at 20-30 US and international sites who have tested positive for SARS-CoV-2 and consenting them to up to 4 fingersticks, the collection of 9 mL of venous blood and responding to a set of standardized questions. All these activities will take place during a single study visit. The whole blood from the fingersticks will be used to test for SARS-CoV-2 antibodies using 2 POC tests, both of which have a CE mark, emergency use authorization (EUA) from the US Food and Drug Administration (FDA) and are Clinical Laboratory Improvement Amendments of 1988 (CLIA) waived. Participants and their providers will be instructed that the results of these tests are not to be used for patient management and the results of the tests will not be shared with participants or their providers. The 9 mL of blood will be processed locally and shipped to a central repository in the US where it will be labeled with a specimen code that can only be matched to the participant's other data using a participant identifier at the Statistical and Data Coordinating Center at the University of Minnesota (UMN). UMN will only have the specimen code and the participant identifier: the matching of the participant identifier to a participant can only be done at the sites.

In addition to this cross-sectional study (also referred to as the field test below), a nested case-control study utilizing specimens already collected from participants in the Therapeutics for Inpatients with COVID-19 (TICO) trial will be conducted. Participants in the TICO trial have already consented to the use of their specimens for future research on COVID-19. The POC tests will be conducted on these specimens and compared to results that have already been generated using an assay at a central laboratory called the GenScript cPass assay (referred to here as the GenScript assay).

The 2 POC assays that will be investigated under this protocol are the LumiraDx SARS-CoV-2 Antibody Test and the RightSign COVID-19 IgG/IgM Rapid Test. Both platforms will be used on all specimens. It is not the goal of this study to impact the indications for either test.

The primary objective of the field test is to test for an association between the outcome of the locally obtained POC test and the centrally obtained result from the GenScript assay on a blood sample obtained at the same time as the sample for the POC tests.

The primary objective of the nested case-control study is to test for an association between the POC test result on stored baseline specimens and the primary efficacy outcome in TICO on a subset of specimens from TICO participants for whom the GenScript assay result has already been determined. Since conducting POC assays on large numbers of stored specimens is time consuming (since each assay takes 10-20 minutes and

each individual specimen must be analysed), a case-control design will be utilized. The case definition is death or time to sustained recovery that exceeds 28 days. To maximize the difference between cases and controls, controls are defined as those with a time to sustained recovery of no more than 16 days. With these definitions there are 68 cases and 77 controls for a total sample size of 145. Of these participants, 104 experienced a sustained recovery (the primary outcome in TICO) and 20 died.

DURATION

Participants in the cross-sectional study will be completed with the study within 24 hours of consent. Actual participation will just involve the consent process, 2 POC tests, and completion of a case report form (CRF) and a blood draw, thus we expect participation to last no more than a few hours.

SAMPLE SIZE

Sample size for the cross-sectional study is targeted at 375. With this sample size the study will have 83% power for detecting a difference in the probability of a positive test between 2 assays when the odds ratio for the 2 assays is 2.6 and the smaller of the 2 probabilities of test discordance is 3%.

The sample size for the nested case-control study is 145. Analysis of the case-control population using the GenScript assay detected a sub-hazard ratio of 1.91. With a sub-hazard ratio of 1.91, 104 events provide 90% power for rejecting the null hypothesis that the sub-hazard ratio is 1 and this number of events provides 80% power for a sub-hazard ratio of 1.75.

POPULATION

The population for the field test was selected to match that of those participating in the TICO trials from which the case-control specimens were selected. This population consisted of adults hospitalized for COVID-19 with symptoms being present no more than 12 days. Participants needed to have a positive test result within 3 days or a positive test more than 3 days prior to randomization and progressive disease suggestive of ongoing SARS-CoV-2 infection. Participants must not have received neutralizing monoclonal antibodies (nMabs), SARS-CoV-2 hyperimmune intravenous immunoglobulin (hIVIG), or convalescent plasma. For this protocol participants must not have received these compounds within 6 months prior to collection of the blood samples for this protocol. Participants with severe disease (as defined by a list of conditions and interventions) are also excluded to be consistent with the TICO trials from which specimens will be used.

2 Introduction

2.1 Study Rationale

A platform trial of therapeutics for patients hospitalized for COVID-19 entitled “A Multicenter, Adaptive, Randomized, Blinded Controlled Trial of the Safety and Efficacy of Investigational Therapeutics for Hospitalized Patients with COVID-19”, referred to as Therapeutics for Inpatients with COVID-19 (TICO), has undertaken the investigation of 6 treatments thus far. TICO trials of bamlanivimab, sotrovimab (also known as VIR-7831), and BRII-196/198, a meta-analysis that included these trials, a trial of hIgIG, and the RECOVERY trial have identified the potential for baseline antibody levels to impact safety and efficacy outcomes with administration of nMab therapy^{1,2,3,4,5,6}. The TICO trial of bamlanivimab found a statistically significant interaction for the primary efficacy outcome, and the TICO trial of BRII-196/198 was consistent with such an interaction. These studies have found that while there may be a benefit for patients who have not yet mounted an antibody response, patients with endogenous antibody probably do not benefit from this treatment, and this may result in misuse of resources and expose patients to unnecessary toxicity, increased costs, and treatment delays. Moreover, in addition to affecting response to therapy, results from the TICO trials also demonstrate that baseline antibody levels were predictive of safety and efficacy outcomes in the placebo group: those with endogenous antibody had better outcomes.

In the TICO trials, antibody levels were assessed using a surrogate neutralizing antibody assay that detects the ability of antibodies to block the interaction of the receptor binding domain (RBD) of the spike protein with the host ACE-2 receptor (the GenScript cPass assay, referred to as the GenScript assay here). While these results point to promising approaches to the provision of care, these results are of limited clinical value as the use of this assay for patient management is extremely challenging due to time and laboratory requirements. This is due to the requirement that the assay be run in batches at a central laboratory, and this delays the determination of the presence of endogenous antibody. Given the urgency of treatment early in the course of disease, this delay could impact patient outcomes.

There are a large number of POC antibody tests with an EUA from the FDA available for detection of antibodies to SARS-CoV-2, thereby presenting an opportunity to rapidly determine if a patient has endogenous antibodies, which can then be used for patient management. Under the current EUAs, these tests only produce a qualitative interpretation of serostatus. This limits their ability to be used for participant management as the cut-offs are generally selected to optimize specificity. Optimization of specificity is sensible for an assay designed for large scale screening, where false positives are the primary concern. In contrast, if there is a safety concern associated with administration of nMabs to those who are seropositive, false negatives are the primary concern. Hence, there is interest in studying POC antibody tests that produce a rapid quantitative result so that the operating characteristics of different cut-offs can be investigated. This would inform using other cut-offs for timely patient management.

There are 2 aspects of a POC testing platform of interest when designing a trial that may use such a test for patient management: 1) performance of the POC test in a hospital setting where patients would be consented and screened for enrolment; and 2) the ability of the results from the POC test to reproduce the association of baseline antibody levels with clinical outcomes that has been found with the GenScript assay. While the former will be examined prospectively at clinical sites that enroll patients, the latter will use stored specimens from completed TICO trials for expeditious evaluation of the association of POC test results with major TICO outcomes in the context of treatment with nMabs (e.g., a 90-day composite safety outcome and time to sustained recovery, the primary endpoint of TICO trials). Ideally, one would want to determine if

there is an interaction between the result of a POC antibody test and outcomes of interest in TICO, as was found using the GenScript assay, but this would require analysing a larger number of stored specimens than is practical to have acceptable power. As a compromise, here we focus on detecting an association between baseline antibody status using the POC test results and safety and efficacy outcomes of interest in TICO among those in the placebo group from completed TICO trials. The hypothesis to be tested here is that those with endogenous antibody as determined by the POC assay will have better outcomes as was observed using the GenScript assay.

This protocol will examine 2 POC platforms: the LumiraDX and the RightSign platforms. Both platforms have a US FDA EUA and a CE mark for a CLIA-waiver when used on fingerstick whole blood. The LumiraDX platform provides a qualitative result in 10-20 minutes and can also provide a quantitative assessment, but this cannot be provided at the POC at this time. (A quantitative POC test is currently under development by the manufacturer). The RightSign platform is exclusively qualitative with a 10-20-minute turnaround time. Table 1 provides further information and links to more detailed information about each assay. Both assays are certified under the CLIA, 42 U.S.C. §263a, that meet requirements to perform medium complexity tests. Nothing is known at this time about the performance of either assay on emerging variants of concern.

| Date EUA Issued or Last Updated | Entity | Diagnostic (Most Recent Letter of Authorization) and Date EUA Issued | Attributes ³ | Authorization Documents ² | Antigen in the assay used to detect antibodies | Readout |
|---------------------------------|------------------------------------|--|--|--------------------------------------|--|---|
| 08/02/2021 | LumiraDx UK Ltd. | LumiraDx SARS-CoV-2 Ab Test 08/02/2021 | Total Antibody (Ab), Fluorescence Immunoassay, Fingerstick Whole Blood | HCP, Recipients, IFU | RBD and S-protein mixture | A dedicated fluorescence detector reads total Ab (immunoglobulin G [IgG], immunoglobulin M [IgM] and immunoglobulin A [IgA]); qualitative |
| 12/21/2020 | Hangzhou Biotest Biotech Co., Ltd. | RightSign COVID-19 IgG/IgM Rapid Test Cassette 06/04/2020 | IgM and IgG Lateral Flow, Fingerstick Whole Blood | HCP, Recipients, IFU | RBD | One IgG band and one IgM band |

Table 1: Further information about the 2 POC assays to be investigated under this protocol.

2.2 Background

TICO is a platform trial designed to efficiently identify treatments for adults who have been hospitalized with COVID-19. A manuscript providing details on the protocol has been published⁷ so here a brief description of the trial is provided. As a platform trial, multiple agents can be investigated simultaneously which allows for efficiencies due to a shared placebo group. Each investigational agent is studied in a randomized placebo-controlled trial with an early futility assessment based on two 7-category ordinal outcomes assessed at day 5 of follow-up to assess efficacy and a composite of grade 3 and 4 adverse events (AEs), serious adverse events (SAEs), clinical organ failure or serious infection or death through day 5 to assess safety. The primary efficacy outcome is time to sustained recovery, which is the first time after

randomization at which someone returns to their pre-hospitalization residence and stays there for 14 days prior to day 90. All-cause mortality through 90 days of follow-up is an important secondary outcome.

Thus far, 6 agents have entered the platform trial with the first 4 being nMabs or combinations of nMabs. These agents are as follows:

1. Bamlanivimab.
2. Sotrovimab (also referred to as VIR-7831).
3. BRII-196/198.
4. AZD7442.
5. MP0420.
6. PF-07304814.

The study has been completed and papers have been written describing the outcomes for the first 3 compounds, while the results for the remainder are still blinded. These 3 trials were stopped for futility at the time of the early futility assessment. Baseline antibody results are available for the first 3 compounds using the GenScript assay.

Analyses of the qualitative GenScript results from participants in the placebo arm of the first 3 trials (n=320) found that being seropositive was associated with superior efficacy and safety outcomes. Competing risk regression was used to test for an association between the baseline qualitative result from the GenScript assay and time to sustained recovery. The result was statistically significant with a sub-hazard ratio of 1.45 and a 95% confidence interval (CI) of (1.17, 1.81). The estimated hazard ratio for death (positive/negative) was 0.17 with a 95% CI of (0.05, 0.57), hence also statistically significant⁶.

While the semi-quantitative GenScript results do not have any authorization for use in patient management, there is evidence that the use of different thresholds for dichotomizing this semi-quantitative result leads to different estimates of the magnitude of the association between the antibody test and time to sustained recovery. By using a lower threshold for antibody levels and thereby reducing the specificity and increasing the sensitivity for being seropositive, one detects a stronger association. The threshold used for the qualitative result finds that 46% of the 320 participants in the placebo arm are seropositive. If the threshold is lowered so that 58% of the participants are seropositive, we find that the sub-hazard ratio increases from 1.45 to over 1.6.

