A nested case-control study will also be conducted to allow for testing of the association between antibody levels at baseline, as assessed by the POC tests and safety and efficacy outcomes among participants randomized to the placebo group in the bamlanivimab, sotrovimab, and BRII-196/198 trials of TICO. The case definition is death or time to sustained recovery that exceeds 28 days. To maximize the difference between cases and controls, controls are defined as those with a time to sustained recovery of no more than 16 days. With these definitions there are 68 cases and 77 controls for a total sample size of 145. Among these participants, 104 experienced a sustained recovery and 20 died.

Conduct of this nested case-control study will require use of the POC assay on stored specimens. One cannot conduct such tests in a batched fashion which makes this analysis time consuming. This testing will be facilitated by procuring multiple POC platforms at a central location. The use of multiple platforms will allow for multiple tests to be conducted in parallel which is more efficient since each specimen must be run one at a time, and each takes 10-20 minutes.

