3.2.2 Central laboratory

The overall objective of central testing of stored specimens is to understand the impact of baseline serology, as assessed by the POC tests, on outcomes of relevance for the TICO trial. The **primary objective** is to test for an association between the POC test result on stored baseline specimens and the primary efficacy outcome in TICO on a subset of specimens from TICO participants for whom the GenScript assay has result has already been determined. Secondary objectives are as follows:

1. Test for an association between each POC test result on stored baseline specimens and efficacy/safety outcomes in TICO in a case-control design.
2. Compare the POC test results to the GenScript results and other antibody test results such as those from Bio-Rad and Quanterix that have already been obtained for these stored specimens.
3. Select a threshold for the quantitative LumiraDX result to optimize the association between the dichotomized assay result and safety and efficacy outcomes using the stored specimens.
4. Compare the 2 POC platforms to each other and the GenScript result using locally (at each site) and centrally determined POC results.
5. Examine associations between these antibody assays and antigen assays which have already been obtained for the stored specimens.
6. Determine the effect of vaccination and other participant characteristics on the antibody test results.

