3.3.3 Case-control comparison

An analysis of the qualitative GenScript result with the 145 patients that will be used for the nested case-control study found a significant difference ($p=0.002$) in the time to sustained recovery, with a sub-hazard ratio of 1.91 (95% CI: 1.35, 2.7) for baseline serostatus, indicating that seropositive patients had a quicker time to sustained recovery. (This used the Fine-Gray approach to modelling competing risks). The quantitative result from this assay also demonstrated a statistically significant association with time to sustained recovery and adjustment for study level effects did not impact the associations meaningfully. An analysis of case control status also detected an odds ratio that was significantly different from 1 ($p=0.015$) with an odds ratio of 2.34 (95% CI: 1.18, 4.65).

With a sub-hazard ratio of 1.91, 104 events provide 90% power for rejecting the null hypothesis that the sub-hazard ratio is 1, and this number of events provides 80% power for a sub-hazard ratio of 1.75. An analysis of case control status has lower power and would require an odds ratio of 2.72 to have 80% power for detecting an association between baseline antibody levels and case control status with this sample size (larger than what was observed for the GenScript assay).

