4.5 Analysis of the Quantitative Results from the LumiraDX Assay

All comparisons that were conducted using the qualitative result from the LumiraDX assay will be repeated using the quantitative result using the appropriate modification of the analysis to accommodate a continuous variable. Comparisons to the RightSign and qualitative GenScript results will use the Wilcoxon rank sum test with the 2 groups being determined by the outcomes of the RightSign or GenScript test (i.e., the ranks of the LumiraDX results for positive and negative results for the other assays will be compared). Adjusted analyses will be pursued using linear regression after transformation (e.g., logarithmic), if appropriate. Comparisons of the locally and centrally conducted LumiraDX assay will be conducted using linear regression with adjustments made by the inclusion of relevant covariates. The quantitative result will also be used in the competing risk regression models as a continuous covariate and as a set of indicator variables that represent the quartiles of the distribution of this assay (to avoid the linearity assumption).

Other approaches to dichotomizing the quantitative LumiraDX results will be investigated and assessed. Potential values to use for dichotomizing the results will be based on deciles of the distribution and for each potential threshold the sub-hazard ratio for the impact of baseline serostatus on time to sustained recovery will be computed. An alternative cut-off may be selected if there are substantial differences in the hazard ratios.

5 Protection of Human Subjects and Other Ethical Considerations

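### Section 4.5 compares LumiraDX decile cut-offs only by the size of the sub-hazard ratio, a yardstick that favors the imprecise end deciles and yields an optimistic ratio

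*Combined protocol and SAP*

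**What the plan says.** Secondary objective 3 in Section 3.2.2 is to "Select a threshold for the quantitative LumiraDX result to optimize the association between the dichotomized assay result and safety and efficacy outcomes", using the stored case-control specimens. Section 4.5 gives the method. On candidates: "Potential values to use for dichotomizing the results will be based on deciles of the distribution". On the quantity to compare: "for each potential threshold the sub-hazard ratio for the impact of baseline serostatus on time to sustained recovery will be computed". On the decision: "An alternative cut-off may be selected if there are substantial differences in the hazard ratios".

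The section names no fit statistic, precision requirement, minimum group size, allowance for having examined nine cut-offs, or validation step for this choice. It does plan, separately, to enter the quantitative result in the competing-risk model as a continuous covariate and as quartile indicators.

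Section 2.2 is background on a different assay. It notes for GenScript that "the use of different thresholds for dichotomizing this semi-quantitative result leads to different estimates of the magnitude of the association". It reports that lowering the GenScript threshold from 46% to 58% positive raised the sub-hazard ratio from 1.45 to over 1.6, and it reads this as a stronger association.

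**The concern.** A sub-hazard ratio (SHR) from a dichotomized marker changes with the cut-off for reasons unrelated to where a real threshold lies. Two matter here.

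- **Precision.** A cut-off calling 10% or 90% of 145 patients positive leaves 14 or 15 in the smaller group. Its ratio is noisy, so it is more likely than a central one to be the largest by chance.
- **Marker shape.** Under a smooth effect, the ratio reflects the gap between mean marker values above and below the cut. For some distributions that gap widens toward one or both ends.

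Comparing ratios by size alone can therefore show apparently substantial differences where no threshold exists, and can move the cut-off toward an end decile. The ratio then quoted at that cut-off overstates the association. Section 2.1 wants alternative cut-offs studied because they could inform patient management, so the choice should rest on a criterion that compares cut-offs fairly.

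**Working it through.** **Inputs.** Section 3.1: 77 controls (recovered by day 16), 68 cases (death, or recovery after day 28) and 104 recoveries. This leaves 145 − 104 = 41 without sustained recovery and 104 − 77 = 27 late recoveries among the cases. Section 3.3.3: GenScript SHR 1.91. Section 2.2: 46% of 320 positive. Section 4.5: nine decile cut-offs. Section 4.4: alpha 0.05, taken as two-sided. The documents do not give the distribution of the quantitative LumiraDX result, so several shapes were tried.

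**The plan's own figure.** Power = Φ(√(D·p(1−p))·ln SHR − 1.96), with D = 104 and p = 0.5, so √26 = 5.10.
- SHR 1.91: 5.10 × 0.647 − 1.96 = 1.34, power 0.91 (stated: 90%).
- SHR 1.75: 5.10 × 0.560 − 1.96 = 0.89, power 0.81 (stated: 80%).

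Both reproduce.

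**Precision by cut-off.** SE(log SHR) ≈ 1/√(D·p(1−p)).
- 50% positive: 1/√26 = 0.196.
- 20% or 80% positive: 1/√16.64 = 0.245.
- 10% or 90% positive: 1/√9.36 = 0.327.

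The end-to-median ratio, √(0.25/0.09) = 1.67, does not depend on the number of events.

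**True ratio by cut-off, normal marker.** With a log-linear effect, log SHR is roughly slope × φ(c)/(p(1−p)). The gap is 1.596 SD at the median, 1.750 at 20/80% and 1.950 at 10/90%. A slope of 0.29 per SD gives exp(0.29 × gap) = 1.59, 1.66 and 1.76. Scaled to the plan's 1.91 at 46% positive (gap 1.598), the values are 1.91, 2.03 and 2.20.

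**Simulation.** There were 4,000 runs per shape. Each took 320 patients, kept the fastest 77 and slowest 68, counted 104 events and left the 41 non-recovered in the risk set. The slope was set so that the SHR is about 1.91 at 46% positive, except in the no-association row. End decile means the cut-off calling 10% or 90% positive; chance alone would give 2/9 = 22%.

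| Marker | Median SHR at 90 / 50 / 10% positive | End decile has largest SHR | End decile has largest score statistic | Median of the largest SHR |
|---|---|---|---|---|
| Normal | 2.15 / 1.91 / 2.23 | 61% | 14% | 2.77 |
| Uniform | 1.82 / 1.89 / 1.93 | 45% | 7% | 2.50 |
| Bimodal | 1.66 / 1.92 / 1.79 | 38% | 6% | 2.34 |
| U-shaped | 1.68 / 1.89 / 1.79 | 36% | 5% | 2.37 |
| Exponential | 1.59 / 1.88 / 3.03 | 73% | 31% | 3.17 |
| No association | 0.99 / 0.99 / 1.00 | 48% | 35% | 1.29 |
| True threshold at 58% positive | 1.58 / 1.99 / 1.48 | 23% | 2% | 2.28 |

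A separate simulation gave 60% (normal), 45% (uniform), 39% (bimodal) and 48% (no association) for the largest SHR, and 11%, 8%, 5% and 37% for chi-square ranking.

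In every no-threshold row the median of the largest SHR exceeds the medians shown for the individual cut-offs (2.77 against at most 2.23 for the normal marker). That excess is the optimism from selection.

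**Section 2.2 contrast.** For a normal marker the gap is 1.598 SD at 46% positive and 1.605 at 58%. A smooth effect giving 1.45 at the first predicts 1.45 at the second.

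**The case against.** The case for leaving the text alone has real force.

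- The LumiraDX distribution is not given, and a mixture of seronegative and seropositive patients is at least as plausible as one bell curve. For bimodal or U-shaped markers the typical ratio peaks near the middle; for a uniform one it is nearly flat. This stands. In those shapes the pull to the ends comes from sampling error, but it is still there (36-45%).
- Even for a normal marker the systematic rise is 1.76/1.59 ≈ 1.11, which a reader might not call substantial. True, but observed ratios also carry the sampling error, and substantial is left undefined.
- The work is exploratory, and the continuous and quartile models would help to reveal a smooth relation. This lowers the stakes. Section 4.5 does not, however, connect those models to the cut-off decision.
- A reader might infer that an end-decile cut-off is necessarily useless. The documents do not support that: Section 2.1 says false negatives matter most if seropositive patients face a safety risk, so a low cut-off lies in a direction the study means to explore. The objection here is only to the criterion.
- Ranking by chi-square is not neutral either. It weights by p(1−p), which favors central splits; with no association it still picks an end decile in 35% of runs, and it does not correct for searching nine cut-offs. This stands, and is why the fix has more than one part.

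**Conclusion.** The point holds as a cheap improvement to an exploratory secondary objective. Ratio size is the only criterion Section 4.5 states, and it does not compare cut-offs on equal terms. Where it guides the choice and there is no true threshold, end deciles are over-selected in every shape tried and the selected ratio is too large. With a real threshold at 58% positive the over-selection all but disappears (23% against 22%), although the selected ratio is still optimistic.

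Three stronger readings are tempting and are not supported:

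- **That the rule will land on a 10% or 90% cut-off.** Section 4.5 says only that another cut-off may be selected and never says the largest ratio is taken. It favors such cut-offs; it does not dictate them. The simulated percentages assume that the maximum is followed.
- **That the true ratio rises toward both ends for any marker.** That needs a bell-shaped marker with a smooth effect.
- **That the GenScript rise in Section 2.2 is itself this artefact.** Both thresholds are mid-range, where the effect is negligible, so that text needs no change.

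Assumptions: two-sided alpha, proportional sub-hazards, complete 90-day follow-up, no sub-study effect, and the marker shapes listed.

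**What to change.** In Section 4.5:

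1. Keep the decile grid, but rank cut-offs by model fit: the score or likelihood-ratio type chi-square of the competing-risk model.
2. Compare the best dichotomy with the continuous LumiraDX model already planned.
3. Keep the default cut-off unless fit clearly improves, and state beforehand what counts as a clear improvement.
4. Report the sub-hazard ratio at the chosen cut-off with its confidence interval, labeled as descriptive and likely optimistic because it was selected from nine cut-offs.

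The cost is a sentence or two of text; the same models are fitted. The downside is that the reported ratio at the chosen cut-off may be smaller. The change does not by itself correct for the search, which is why the label in step 4 is needed.
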